Adaptive Design: The Steering and Safety Committee and Sponsor will review the accumulating efficacy and safety data at planned intervals, and based upon the safety and efficacy profile of SelK2 may decide to modify enrollment by adding a third study arm testing 7.5 mg/kg SelK2 given in addition to enoxaparin (40 mg, SC, QD) and removal of the SelK2 only arm. The two remaining arms will enroll patients in a 2:1 ratio with two patients receiving SelK2 and Enoxaparin for every one patient receiving Enoxaparin only at doses shown below:

- 1.) 7.5 mg/kg SelK2 (IV, single-dose) and 40 mg Enoxaparin, SC, QD
- 2.) Active Comparator (40 mg Enoxaparin, SC, QD)

Criteria for Selection of Patients:*Inclusion Criteria:*

1. Males or females, between 18 and 80 years of age, inclusive;
2. Females must be non-pregnant and non-lactating, and either postmenopausal (>12 months since last menses) or using highly effective contraceptive measures as defined by the Clinical Trial Facilitation Group (CTFG) guidelines;
3. Males, if engaged in sexual relations with a partner of child-bearing potential, must use highly effective contraceptive measures as defined by the Clinical Trial Facilitation Group (CTFG) guidelines;
4. Planned to undergo elective, primary total unilateral TKA under general anesthesia; and
5. Able to comprehend and willing to give written informed consent.

Exclusion Criteria:

Patients presenting with any of the following will not be included in the study:

1. Body weight <50 kg at Screening;
2. Previous deep vein thrombosis (DVT) of the leg or pulmonary embolism (PE) within the past year;
3. Malignancy within 1 year, except for basal or squamous cell carcinoma of the skin or carcinoma *in situ* of the cervix that has been successfully treated;
4. Myocardial infarction, transient ischemic attack or stroke within the last 6 months;
5. Patients at increased risk of bleeding because of history of increased bleeding tendency (i.e., history of bleeding diathesis) or any other condition that in the opinion of the Investigator increases risk of bleeding (e.g., recurrent gastrointestinal ulcer) or patients with a history of intracranial or intraocular bleeding;
6. Brain, spinal, or ophthalmologic surgery within the past 3 months;
7. Cockcroft-Gault calculated creatinine clearance <30 mL/min at Screening (central lab will calculate the Cockcroft-Gault value);

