Assuming that the rate of VTE for the active comparator (enoxaparin) arm of this study will be 25%, it is estimated that a sample size of 76 evaluable patients per arm should give the study 80% power of declaring non-inferiority between the SelK2 only arm and the enoxaparin active comparator arm. This calculation uses a one-sided 90% CI with a non-inferiority margin of 15%. This calculation assumes that the underlying rate of VTE for the SelK2 and enoxaparin arms will be identical at 25% and with the non-inferiority margin set as the midpoint between the expected active therapy response compared with an assumed placebo event rate in this patient population of 55%. Consequently, making the conservative estimate that up to 20% of randomized patients may not have evaluable endpoint data; a total of 95 patients will be enrolled per arm to provide at least 76 endpoint evaluable patients per arm.

Sample Size Considerations for Adaptive Arm:

With the same assumptions as above for the active comparator (enoxaparin) arm of the study event rate, it is estimated that a sample size of 76 evaluable patients in a combination therapy arm of SelK2 and enoxaparin should give the study 80% power of declaring superiority between the SelK2 and enoxaparin and the enoxaparin active comparator arm for an estimated SelK2 and enoxaparin VTE event rate of 6% (a 19% difference between combination treatment effect and active comparator treatment effect). This calculation assumed a two-sided 0.1 alpha, a Pearson Chi-squared test, and a superiority comparison.

TABLE OF CONTENTS

PROTOCOL SYNOPSIS	iii
1.0 INTRODUCTION	1
1.1 Background	1
1.2 Preclinical Studies Supporting SelK2 Antithrombotic Activity	2
1.2.1 In Vivo Mechanism of Action	2
1.2.2 Toxicology	2
1.2.3 Absorption, Distribution, Metabolism, and Excretion	3
1.3 Clinical Studies of SelK2.....	4
1.4 Study Rationale	7
1.5 Rationale for the Dose Regimen	7
2.0 STUDY OBJECTIVES	8
3.0 STUDY DESIGN	9
3.1 Basic Design Characteristics.....	9
3.2 Number of Patients.....	9
3.3 Study Population	10
3.4 Study Phases.....	10
3.4.1 Screening Phase	10
3.4.2 Treatment Phase.....	10
3.4.3 Follow-Up Phase	11
3.4.4 Study Diagrams for SelK2 and Enoxaparin Arms	11
3.5 Efficacy and Safety Assessments.....	12
3.6 Endpoints	13
3.6.1 Primary Efficacy Endpoint.....	13
3.6.2 Exploratory Efficacy Endpoints	13
3.6.3 Pharmacokinetic Assessments of SelK2	13
3.6.4 Pharmacodynamic Assessments of SelK2	14
3.6.5 Safety Endpoints	14

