3.2 Number of Patients

Approximately 190 patients are planned to be enrolled in this clinical study as designed. Based on adaptive design, if a third cohort of the study is added, an additional 95 patients may be added for a maximum of approximately 285 patients enrolled.

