4.0 SELECTION OF STUDY POPULATION

A total of 190 patients will be enrolled, 95 patients in each of 2 arms of the study (Arm 1: 7.5 mg/kg SelK2, IV or Arm 2: 40 mg enoxaparin, SC, QD).

An additional adaptive arm of 95 patients may be added for the investigation of the combination of 7.5 mg/kg SelK2, IV and 40 mg enoxaparin, SC, QD.

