5.1.3 Randomization Methods and Procedures

Patients will be screened prior to randomization and assigned a Subject ID number by IRT. After patient's eligibility is confirmed, treatment assignment will be determined by a validated central randomization schedule using IRT (Interactive Response Technology). If a patient meets all of the inclusion criteria and none of the exclusion criteria, delegated and approved site personnel, trained on the use of the IRT, will randomize the patient. The IRT system will assign the patient a treatment group based on the next available slot in the randomization scheme. It is important to note that the randomization web entry should **only** be made after eligibility has been established. Prior to randomization, baseline efficacy and safety assessments will be taken.

Patients will be randomly placed into one of two treatment arms:

- 1) 7.5 mg/kg SelK2, IV or
- 2) 40 mg enoxaparin, SC, QD.

Patients will be randomized to these two treatment arms in a 1:1 ratio. Randomization will be stratified by site.

For patients randomized into the 7.5 mg/kg SelK2 arm, the IRT system will calculate the number of vials required based on the patient weight and will provide the user the appropriate vial numbers to use.

Changes in Randomization Procedure when Adaptive arm is activated and enrollment into the SelK2 only arm is discontinued:

When the adaptive arm is activated and the SelK2 only arm is closed, the central randomization process will allow for placing patients randomly into one of the below two treatment arms and randomization will continue to be stratified by site.

Patients will be randomly placed into one of two treatment arms:

- 1) 40 mg enoxaparin, SC, QD, or
- 2) 7.5 mg/kg SelK2, IV and 40 mg enoxaparin, SC, QD.

The randomization ratio will be altered to a 2:1 ratio (2 patients receiving 7.5 mg/kg SelK2 and enoxaparin to every 1 patient receiving Enoxaparin only) so that the total number of patients in each of the two remaining arms will be approximately equivalent at the end of the study. This modified randomization ratio will be controlled by the centralized IRT system.

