10.0 STATISTICAL METHODS AND PLANNED ANALYSES

10.1 Sample Size and Power

Assuming that the rate of VTE for the active comparator (enoxaparin) arm of this study will be 25%, it is estimated that a sample size of 76 evaluable patients per arm should give the study 80% power of declaring non-inferiority between the SelK2 arm and the enoxaparin active comparator arm. This calculation uses a one-sided 90% CI with a non-inferiority margin of 15%. This calculation assumes that the underlying rate of VTE for the SelK2 and enoxaparin arms will be identical at 25% and with the non-inferiority margin set as at the midpoint between the expected active therapy response compared to an assumed placebo event rate in this patient population of 55%. Consequently, making the conservative estimate that up to 20% of randomized patients may not yield evaluable endpoint data, a total of 95 patients will be enrolled per arm to provide at least 76 endpoint evaluable patients per arm.

Sample Size Considerations for Adaptive Arm:

With the same assumptions as above the for active comparator (enoxaparin) arm of the study event rate, it is estimated that a sample size of 76 evaluable patients in a combination therapy arm of SelK2 and enoxaparin should give the study 80% power of declaring superiority between the SelK2 and enoxaparin arm and the enoxaparin active comparator arm for an estimated SelK2 and enoxaparin VTE event rate of 6% (an 19% difference between combination treatment effect and active comparator treatment effect). This calculation assumes a two-sided 0.1 alpha, a Pearson Chi-squared test, and a superiority comparison.

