10.5 Steering and Safety Committee Data Reviews and Interim Analyses

A formal study Steering and Safety Committee will consist of at least 3 clinicians (with experience and expertise in venous thrombosis). The Steering and Safety Committee will be charged with reviewing in an unblinded fashion all accumulating safety and efficacy data to assure overall patient safety in this study.

The following efficacy and safety data will be provided to the Steering and Safety Committee by treatment group, and where appropriate by study visit day and time:

- Overall VTE event rate (as adjudicated);
- Individual component event rate (individual components of the composite VTE event rate);
- Incidence of bleeding events (as adjudicated) including the following will be tabulated by treatment:
 - 1) Major Bleeding event (MB),
 - 2) Clinically Relevant Non-Major Bleeding event (CRNMB),
 - 3) Minor Bleeding even, or
 - 4) Combination of MB and CRNMB
- Incidence of AEs (including SAEs) ;
- Clinical laboratory values (hematology, serum chemistries, urinalysis, and coagulation parameters);
- ECGs; and
- Vital signs.

The Steering and Safety Committee will use all of the above accumulating data to assess the safety of continuing each aspect of this study.

Interim Analyses to support decision on whether or not to recommend activation of Adaptive Arm:

The Steering and Safety Committee is also charged with making recommendations to the Sponsor with regards to the activation of the adaptive arm that investigates the efficacy and safety of SelK2 use in combination with enoxaparin. At certain enrollment milestones, the Steering and Safety Committee will be presented with interim analysis tables which will include VTE event rates by treatment group with 80% confidence intervals and the calculated risk difference (the difference

between the cumulative incidence in the SelK2 arm to that of the cumulative incidence the enoxaparin arm) with 80% confidence intervals. The conditional powers for demonstrating non-inferiority at the end of the trial based upon accumulated data at interim may also be computed. These interim analyses will be part of the data set used by the Committee as they determine whether or not to recommend activation of adaptive arm. This adaptive arm may be initiated if the Steering and Safety Committee determines that preliminary data suggests the potential for an additive effect in VTE reduction and that the combination does not pose an additional safety risk.

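### The 80% power stated for SelK2 plus enoxaparin versus enoxaparin does not match the named test: it gives about 95% with 76 enoxaparin patients and about 86% with 38 concurrent controls

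*Combined protocol and SAP*

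**What the plan says.** The adaptive-arm paragraph of Section 10.1 carries over the 25% enoxaparin VTE rate, assumes 6% on the combination (a 19-point difference), and states that "a sample size of 76 evaluable patients in a combination therapy arm of SelK2 and enoxaparin should give the study 80% power" for superiority. The synopsis gives the same figures and adds: "This calculation assumed a two-sided 0.1 alpha, a Pearson Chi-squared test, and a superiority comparison". Neither place states how many enoxaparin patients enter the comparison.

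Two other statements bear on that number. The main paragraph of Section 10.1 says that "a total of 95 patients will be enrolled per arm to provide at least 76 endpoint evaluable patients per arm". Section 5.1.3 changes the allocation to 2:1 in favour of the combination once the adaptive arm opens, "so that the total number of patients in each of the two remaining arms will be approximately equivalent at the end of the study". Together they point to about 76 evaluable patients in each of the two arms compared. The documents do not say whether enoxaparin patients randomised before activation count in the combination comparison, or only those randomised alongside it.

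**The concern.** A stated power should follow from its stated rates, sample size, alpha and test. Here everything is given except the control number, and neither control number that the design supports yields 80% under the named test.

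What is at stake is how the combination comparison is read. Someone relying on Section 10.1 would conclude that the design can only just detect a fall from 25% to 6%, and would treat smaller effects as out of reach. In fact 76 versus 76 has 80% power for a difference of about 15 points. The missing control number also leaves open a design question worth about 9 points of power: whether all enoxaparin patients are used, or only concurrent ones.

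**Working it through.** **Inputs.** Enoxaparin rate p_E = 0.25; combination rate p_C = 0.06; two-sided alpha 0.10, so z = 1.645; Pearson chi-squared test; n_C = 76 evaluable (all Section 10.1). Non-evaluable allowance 20% (Section 10.1), so 95 × 0.8 = 76.

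**Control number, two cases.**
- All enoxaparin patients: n_E = 76 (Section 10.1, per arm; Section 5.1.3, arms about equal at the end).
- Concurrent only: n_E = 76 / 2 = 38. This is derived from the 2:1 ratio and is not stated in the documents.

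**Formula** (pooled variance under the null, unpooled under the alternative):

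Power = Φ[(|p_E − p_C| − z·s0) / s1], where p̄ = (n_E·p_E + n_C·p_C)/(n_E + n_C), s0 = √[p̄(1 − p̄)(1/n_E + 1/n_C)] and s1 = √[p_E(1 − p_E)/n_E + p_C(1 − p_C)/n_C].

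**A check on the neighbouring figure.** The non-inferiority power in the same section reproduces: 0.15 / √(0.1875 × 2/76) = 0.15 / 0.07024 = 2.135; 2.135 − 1.282 = 0.854; Φ = 80.3%. The mismatch is therefore confined to the adaptive-arm paragraph.

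**76 versus 76.** p̄ = 0.155; s0 = 0.05871; s1 = 0.05665. (0.19 − 1.645 × 0.05871) / 0.05665 = (0.19 − 0.0966) / 0.05665 = 1.649. Power = 95.0%. Exact binomial enumeration of the Pearson test gives 96.4%.

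**38 enoxaparin versus 76 combination.** p̄ = 0.1233; s0 = 0.06533; s1 = 0.07534. (0.19 − 0.1075) / 0.07534 = 1.096. Power = 86.3%; exact 88.6%.

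**What would give 80% under the named test and alpha (same formula).**
- Rates held at 25% and 6%, n_C = 76: n_E = 27 gives 80.3% and n_E = 26 gives 79.6%. No allocation in the documents produces about 27 controls.
- Equal arms: 44 per arm, well below 76.
- 76 versus 76: a combination rate of 9.8% gives 80.1%, a difference of 25 − 9.8 = 15.2 points.
- 38 versus 76: a combination rate of about 7.5% gives 79.8%.

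**Sensitivity to the method.**

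| Method | 76 v 76 | 38 v 76 |
|---|---|---|
| Pearson, alpha 0.10 (as named) | 95.0% | 86.3% |
| Exact Pearson, alpha 0.10 | 96.4% | 88.6% |
| Continuity-corrected, alpha 0.10 | 92.2% | 79.8% |
| Unpooled variance, alpha 0.10 | 95.6% | 81.0% |
| Pearson, two-sided alpha 0.05 | 90.7% | 79.5% |

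With 76 controls, none of these variants comes near 80%. With 38 controls, only the three that depart from the named test or alpha do.

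**The case against.** The strongest reply is that the paragraph never gives the enoxaparin number, so its inputs are incomplete and 80% cannot be called irreproducible. With 38 concurrent controls, a continuity correction (79.8%), an unpooled variance (81.0%) or a two-sided alpha of 0.05 (79.5%) all return about 80%. Section 10.3.1 does set 0.05 as the general default. The sponsor may well have made one of these calculations. That stands as a plausible origin, but it does not rescue the text: both places name a two-sided alpha of 0.1 and the Pearson test, and neither mentions 38 controls or a correction. If that was the calculation, its control number and method still have to be written down.

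A second reply is that 80% can be read as a floor, and that 76 was carried over from the non-inferiority calculation. This also has force: the discrepancy is in the safe direction, and no sample size or decision rule changes. But the text gives 80% as the power for that effect, not as a minimum.

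Two stronger readings are tempting and not supported. A reader might infer that the combination arm is wrongly sized or underpowered; under the plan's own assumptions it is larger than 80% power needs. A reader might also infer that the 80% non-inferiority power is wrong, because activation brings "and removal of the SelK2 only arm". That figure is correct for the 76 per arm it describes, and Section 10.1 does not claim it for a shortened arm. The documents give no closure point, and closure would follow unblinded review, so a fixed-sample power for early closure would rest on numbers the plan does not contain.

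**Conclusion.** The stated 80% is wrong as written. Under the named test and alpha, the power is about 95% (exact 96%) for 76 versus 76, or about 86% (exact 89%) for 76 versus 38 concurrent controls. The first case rests on reading Sections 10.1 and 5.1.3 together as implying 76 evaluable enoxaparin patients; the second rests on strict 2:1 allocation and concurrent controls only. Both keep the plan's rates of 25% and 6%. The power is understated by about 15 points in the first case and about 6 in the second. This is a reporting error in the conservative direction, together with an unstated control set; it is not a flaw in the size of the trial.

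**What to change.** In the adaptive-arm paragraph of Section 10.1 and in the synopsis, state three things: the number of evaluable enoxaparin patients, whether the control set is all or only concurrent enoxaparin patients, and the power formula, including any continuity correction. Then restate the power as about 95% for 76 versus 76 (equivalently, 80% for 25% versus about 10%), or about 86% for 76 versus 38 if only concurrent controls are used. If a different method or alpha was intended, name it and give the power that follows from it.

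Optionally, add one sentence that the 80% non-inferiority power applies only if the SelK2-only arm reaches 76 evaluable patients.

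The cost is a text change in two places, with no added patients and no change to the conduct of the trial.

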10.2 Analysis Populations

Assignment of patients to analysis populations will be done prior to clinical data lock for the study. The following populations will be defined: Intent-to-Treat (ITT), modified Intent-to-Treat (mITT), Per-Protocol (PP), and Safety.

Intent-to-Treat (ITT): All patients who are randomized. The ITT population will be analyzed by randomized treatment group.

Modified Intent-to-Treat (mITT): All patients in the ITT population who also have a successful venogram or symptomatic VTE event which allow for assessment of the primary efficacy outcome.

Per-Protocol (PP): All mITT patients who complete the study and have no major protocol violations that will impact the efficacy assessments.

Safety: All patients who received at least 1 dose of study drug. Safety population will be analyzed by actual treatment received.

